### **10.3. Analysis of Exploratory Endpoints**

Several exploratory analyses will be employed to investigate phenotypic characteristics associated with response to intervention, and the association of biomarkers with outcomes, to maximize the scientific knowledge gained from this study. For example, exploiting the longitudinal measures of the phenotypic characteristics, we will jointly model longitudinal and event time (e.g., response to treatment) as a function of treatment group and other potential prognostic factors. We will also use more sophisticated statistical models, such as linear and/or non-linear mixed effects models or nonparametric regression, to explore the relationship of phenotype and response to treatment, and biomarkers with clinical outcomes.

### **10.4. Safety Analysis**

Adverse events and laboratory parameters will be summarized by treatment group. Chi-square or Fisher's exact tests will compare salsalate to placebo for discrete outcomes, and two-sample

t tests (on appropriately transformed continuous outcomes, if necessary) or nonparametric wilcoxon tests will assess treatment differences for continuous outcomes. Serious adverse events (SAEs), unexpected adverse events and all AEs will also be summarized descriptively by body system and treatment group, regardless of relatedness to study treatment.

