**Table 1: Proposed Visit Schedule for TINSAL-T1DN Study**

Visit Number	Visit 1	Visit 2	Visit 3	Visit 4**	Visit 5	Visit 6**	Visit 7
Visit Description	Screening	Baseline	Monitoring	Monitoring	Monitoring/ Outcomes	Monitoring	Monitoring/ Outcomes
Time point	Day -180 to 0	Day 0	Month 1	Month 3	Month 6	Month 9	Month 12
Visit window		NA	± 7 days	± 14 days	± 14 days	± 14 days	± 14 days
Informed Consent	X						
Medical History /Physical Examination†	X	X		X	X	X	X
Laboratory Measures*	X			X	X	X	X
Skin Biopsies (proximal/distal leg)		X					X
Neurological History /Physical Examination†	X						X
Nerve Conduction Studies	X						X
Neuropathy Total Symptom Score	X	X			X		X
Cardiovascular Autonomic Studies		X					X
Resting Heart Rate		X	X	X	X	X	X
Quantitative Sensory Testing	X						X
NeuroQOL		X			X		X
Survey of Autonomic Symptoms		X			X		X
Neuropathy Pain Scale		X			X		X
Functional Assessments							
Berg Balance Scale							
8-foot Get Up and Go Test		X					
Modified Falls Efficacy Scale							X
Medication Dispensing§		X		X	X	X	
Medication Compliance			X	X	X	X	X
Medication Return				X	X	X	X
Adverse Events Monitoring		X	X	X	X	X	X

† Baseline history and examination will include diabetes duration, diabetes complications, diabetes treatment, concurrent medical problems, relevant past surgical history, height, weight, blood pressure and pulse, and foot examination. Follow up visits will include changes in medical or surgical history, weight, blood pressure, pulse and foot examination \* HbA1c, Metabolic Comprehensive Panel, Complete Blood Count with Platelets, TSH, Lipid Profile, Cystatin-C, Uric Acid and Urine Albumin performed at screening visit (unless results for these tests are documented in the medical record as being done in the prior 3 months for all except HbA1c (1 month) and Urine Albumin (6 months). Urine pregnancy test at screening for all women of childbearing potential regardless of contraceptive practiced. HbA1c, Metabolic Comprehensive Panel, CBCP, Cystatin-C, Uric Acid and Urine Albumin will be repeated at 3, 6, 9 and 12 months of follow-up. Lipids will be repeated at 3, 6 and 12 months of follow-up. Luminex inflammatory marker assays on blood and urine performed at screening or baseline, and again at study end.

\*Visit windows for visit 3-7 are based off when the patient starts the study medication following visit 2 due to the shipping of the medication from Belmar Pharmacy directly to the participant.

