### 3. TRIAL DESIGN

This is a phase II-III, multi-site randomized, double-blind, placebo-controlled clinical trial to evaluate the effect of salsalate on measures of small fiber neuropathy in 70 subjects with T1DM and mild DN. In the original study design we proposed to randomize up to 60 subjects in a 1:1 fashion to up to 3 grams of salsalate or matched placebo. In August 2017 the protocol was modified by recommendation of the DSMB to address differential study medication discontinuation rates and to increase the number of subjects exposed to study drug. Specifically, the protocol will enroll up to 70 subjects and randomize them in a 3:2 fashion to

salsalate or placebo. All subjects enrolled subsequent to the approval of the revised protocol will be randomized in 3:2 fashion, up to 3 grams per day of salsalate or placebo respectively. Treatment duration will be 12 months. Randomization will be stratified by baseline HbA1c ( $\leq 8.0$  or  $> 8.0\%$ ) and by gender within the HbA1c groups. Subjects will be evaluated every 3 months for a total of 12 months.

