### **6.1. Recruitment/Screening**

#### Visit 1: Screening/Eligibility

An eligibility visit will be scheduled for subjects who, based on preliminary screening (telephone, email, medical chart review) meet the general entry criteria (age, T1DM, diabetes duration, symptomatic peripheral neuropathy, no contraindications for salsalate, etc.). At visit 1 the investigator or her designee will obtain written informed consent, after which all required eligibility examinations will be performed. The eligibility examination will include the following laboratory assessments: HbA1c, metabolic comprehensive panel (METCOMP), complete blood count with platelets (CBCP), thyroid stimulating hormone (TSH), lipid profile, cystatin-C, uric acid, urine albumin assessment, and in all women of child bearing age and potential, a urine

pregnancy test, even if an accepted method of contraception is being used. If any of the required laboratory measures are documented in the subject's medical record as being completed in the prior 3 months (1 month for HbA1c, and 6 months for urine albumin), they will not need to be repeated at the screening visit. Additional blood and urine will be obtained for Luminex assays of inflammatory markers. The Luminex assays though may be postponed until the baseline examination.

Weight, height and seated blood pressure and pulse will be obtained.

A structured neurologic history and physical examination and nerve conduction studies will be performed at the screening visit to verify and document the presence of signs or symptoms of peripheral neuropathy, the presence of a sural nerve response, and abnormality of at least one abnormal nerve attribute (amplitude, latency, conduction velocity or f-wave) in the sural, peroneal or ulnar nerve. In the absence of a sural nerve response (e.g., sural amplitude is 0  $\mu$ V, response is unobtainable, then the presence of a peroneal motor nerve conduction velocity of  $\geq$  35 meters per second will be required for inclusion. Quantitative sensory testing will also be conducted at the screening visit.

All visit 1 measures are ideally to be completed within a 4-week time frame but may take up to 6 months (180 days) if repeated measures are needed, and may be done at one, or over several visits if that is more convenient for the subject.

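### Section 10.4 plans unadjusted two-sample tests for laboratory safety outcomes without naming the scale or the visit; adjusting for the screening value would narrow the confidence intervals at no data cost, by a small to large amount

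*Combined protocol and SAP*

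**What the plan says.** Section 10.4 covers laboratory safety in two statements. The first is descriptive: "Adverse events and laboratory parameters will be summarized by treatment group". The second is inferential: two-sample "t tests (on appropriately transformed continuous outcomes, if necessary) or nonparametric wilcoxon tests will assess treatment differences for continuous outcomes". No visit, change score, covariate, repeated-measures model or confidence interval is mentioned. Section 7.2 defines safety as adverse events plus laboratory parameters, so these statements govern the whole laboratory half of the safety assessment.

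The footnote to Table 1 sets out what is collected. Before treatment there is one set, with "Complete Blood Count with Platelets, TSH, Lipid Profile, Cystatin-C, Uric Acid and Urine Albumin performed at screening visit" alongside HbA1c and the metabolic panel. After that, "HbA1c, Metabolic Comprehensive Panel, CBCP, Cystatin-C, Uric Acid and Urine Albumin will be repeated at 3, 6, 9 and 12 months of follow-up", and "Lipids will be repeated at 3, 6 and 12 months of follow-up". TSH is not listed again after screening.

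The efficacy analyses in section 10.2 use such data more fully. The primary model has baseline nerve fiber density as a covariate, and repeated continuous secondary outcomes get a mixed model. Section 10 leaves detailed methods to a Statistical Analysis Plan to be finalized before unblinding; the text available for review contains no further detail on laboratory safety.

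**The concern.** A two-sample test takes one number per subject. With a screening value and up to four follow-up values available, someone must decide what that number is, and section 10.4 leaves the choice open. There are two consequences.

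First, scale and visit could be settled after the data are seen. Second, no version of the planned test adjusts for the screening value. In a trial of 70 subjects, of whom 56 to 59.5 remain at the assumed 15-20% attrition (70 × 0.80 and 70 × 0.85), intervals for creatinine, cystatin-C or urine albumin will be wide, and precision that can be had for nothing is worth having. The laboratory comparison also feeds any risk-benefit analysis that the DSMB may request under section 10.5.

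**Working it through.** **The plan's own figures.** The protocol gives no power or precision for any laboratory outcome, so there is nothing on this point to reproduce. Its only power figure, 81% for the primary outcome (25 per group, difference 1.65, SD 2.0, two-sided 5%), comes out at 81.5% with the noncentral t distribution.

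**Inputs.**
- From the documents: 70 subjects, 20% attrition, 3:2 allocation, and follow-up laboratory visits at four time points (three for lipids).
- Assumed: equal variances at all visits, a common correlation r between any two visits, r = 0.5 to 0.8, and 3:2 allocation throughout. Section 3 applies 3:2 only to subjects enrolled after the August 2017 revision.

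**Variance of the treatment difference, relative to a t test on raw values at one visit.**
- t test on change from screening: 2(1 − r)
- ANCOVA at one visit: 1 − r²
- ANCOVA on the mean of four follow-up visits: (1 + 3r)/4 − r²

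The ratio of one-visit ANCOVA to the change-score test is (1 − r²)/[2(1 − r)] = (1 + r)/2. Interval widths scale with the square root.

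| r | 1 − r² | ANCOVA interval narrower than raw t | (1 + r)/2 | ANCOVA interval narrower than change t | Four-visit mean: variance | Narrower than raw t |
|---|---|---|---|---|---|---|
| 0.5 | 0.75 | 13% | 0.75 | 13% | 0.375 | 39% |
| 0.7 | 0.51 | 29% | 0.85 | 8% | 0.285 | 47% |
| 0.8 | 0.36 | 40% | 0.90 | 5% | 0.21 | 54% |

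For lipids, with three visits, the last formula becomes (1 + 2r)/3 − r². At r = 0.7 this is 0.80 − 0.49 = 0.31, or 44% narrower than the raw test.

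**Worked example.** Twenty percent attrition leaves 56 subjects; 56 × 3/5 ≈ 34 and 56 × 2/5 ≈ 22. Take SD 15 (an arbitrary assumed unit) and r = 0.7. The 95% half-widths are:
- raw value at one visit: 2.005 × 15 × √(1/34 + 1/22) = 8.2
- change from screening: 8.2 × √0.6 = 6.4
- ANCOVA at one visit: 8.2 × √0.51 = 5.9
- ANCOVA on the four-visit mean: 8.2 × √0.285 = 4.4

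**Power illustration.** With 50 completers split 30:20 and a constant shift of 0.5 SD, a raw-value test at one visit has 39.7% power. At r = 0.5, 0.7 and 0.8:
- t test on change: 39.7%, 59.1%, 76.5%
- ANCOVA at one visit: 50.0%, 66.2%, 80.7%
- ANCOVA on the four-visit mean: 79.1%, 88.9%, 95.9%

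**Where the repeated visits help.** With complete data, a mixed model with unstructured covariance estimates the month-12 difference about as precisely as month-12 ANCOVA. Most of the gain from repeated visits therefore comes from reporting an average over follow-up. A t test on the average change from screening captures part of that gain too: its relative variance is (1 + 3r)/4 + 1 − 2r = 0.375 at r = 0.7, against 0.285 for ANCOVA.

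**The case against.** Four stronger readings are tempting, and the documents support none of them.

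- **That the plan ignores the screening value.** Section 10.4 is silent on scale, and a t test on change would use it. On that reading the loss against one-visit ANCOVA is only 5% to 13% in interval width.
- **That only month 12 is tested.** No visit is named. The same tests could be run at each of months 3, 6, 9 and 12, and laboratory values are in any case to be summarized by group.
- **That laboratory data are lost unequally between arms.** Section 3 says the allocation was revised "to address differential study medication discontinuation rates". That concerns stopping tablets. Section 5.2.4 keeps all subjects in follow-up unless consent is withdrawn or the investigator judges continued participation unsafe. The documents report no differential loss of laboratory values.
- **That the comparison is far less precise than it could be.** This needs raw values and a high r. Screening may be old: visit 1 measures "may take up to 6 months (180 days) if repeated measures are needed", and results from the preceding 1 to 6 months may be used instead, depending on the test. Eligibility limits on creatinine, eGFR and urine albumin also narrow the range. Each could lower r for the renal measures.

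It is also fair to say that simple two-group tests are valid under randomization, that no stated error rate or power depends on them, and that the separate analysis plan may supply the detail. All of this stands and limits the size of the point. It does not remove it: scale and visit are undefined in the text available, and under the assumptions above ANCOVA is, in large samples, at least as precise as either candidate t test.

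**Conclusion.** The point holds as a worthwhile improvement in efficiency and specification. It does not show bias or an invalid test. Section 10.4 leaves the tested laboratory quantity undefined and plans no screening-adjusted or longitudinal estimate, although the data are collected and section 10.2 uses such models for efficacy.

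The size depends on two unknowns: which quantity would be tested, and r. If raw values are tested, adjustment is worth a moderate to large narrowing; if change is tested, the one-visit gain is small and the larger gain lies in averaging over visits. These figures rest on equal variances and a common correlation. The benefit of averaging also presumes a roughly constant shift over follow-up; an effect that appears late would be diluted in the average, which is why the visit-specific estimates are needed as well.

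**What to change.** In section 10.4 or the analysis plan, before unblinding:

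- Define the pre-treatment value as the last one before the first dose. Appendix A already has laboratory measures repeated at visit 2 after a long delay.
- For laboratory measures with follow-up values, replace the two-sample tests with a model adjusted for the screening value and HbA1c stratum. Use either a repeated-measures mixed model with visit as a category and treatment by visit, or ANCOVA at each visit. TSH has no scheduled follow-up value and is outside this.
- Log-transform skewed measures such as the urine albumin ratio.
- Report adjusted differences with 95% confidence intervals at each visit and for the average over follow-up visits.
- Keep Wilcoxon tests as a check, and Fisher or chi-square tests for adverse events.

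The cost is a paragraph of text, a little programming and some reliance on model assumptions. No new data are needed.

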## **10.5. Interim Analysis**

Given the expected enrollment period of 2 years and the 1-year follow-up period, an interim analysis to stop study enrollment for benefit or futility is not feasible. Rather, periodic assessment of the safety of study subjects will be undertaken by an independent Data and Safety Monitoring Board (see below). Although salsalate is an approved medication (off-label for this indication), if there were safety concerns in this study, the DSMB could request a formal analysis of safety and efficacy data to delineate the risk-benefit profile of salsalate in this study, with the potential to stop the study.

## **10.6. Data and Safety Monitoring Board**

Study monitoring will be done by the Michigan Institute for Clinical and Health Research (MICHR). A Data and Safety Monitoring Board (DSMB) will oversee this study. Members of the DSMB are independent of the study investigators and represent Endocrinology, Neurology, Biostatistics, as well as possibly a lay member. The DSMB will meet every three months or more frequently if requested by the Chairs either in person or by teleconference. This protocol will be approved by the DSMB prior to initiation of recruitment.

# **11. DATA HANDLING AND RECORD KEEPING**

## **11.1. Case Report Forms / Electronic Data Record**

As used in this protocol, the term case report form (CRF) should be understood to refer to either a paper form or an electronic data record or both, depending on the data collection method used in this trial.

A CRF is required and should be completed for each included subject. It is the investigator's responsibility to ensure completion and to review and approve all CRFs. CRFs must be signed by the investigator or by an authorized staff member. These signatures serve to attest that the information contained on the CRFs is true. At all times, the investigator has final personal responsibility for the accuracy and authenticity of all clinical and laboratory data entered on the CRFs. Subject source documents are the physician's subject records maintained at the trial site. In most cases, the source documents will be the hospital's or the physician's chart. In cases where the source documents are the hospital or the physician's chart, the information collected on the CRFs must match those charts.

In some cases, the CRF may also serve as the source document. In these cases, the DCC and the investigator must prospectively document which items will be recorded in the source documents and for which items the CRF will stand as the source document.

## **12. ETHICS**

### **12.1. Institutional Review Board (IRB)**

It is the responsibility of the investigator to obtain prospective approval of the trial protocol, protocol amendments, informed consent forms, and other relevant documents, e.g., advertisements, if applicable, from the IRB. All correspondence with the IRB should be retained in the Investigator File.

### **12.2. Ethical Conduct of the Trial**

The trial will be performed in accordance with the protocol, International Conference on Harmonization Good Clinical Practice guidelines, and applicable local regulatory requirements and laws.

### **12.3. Subject Information and Consent**

The informed consent form must be agreed to by the Protocol Committee and the IRB and must be in compliance with ICH GCP, local regulatory requirements, and legal requirements.

The investigator must ensure that each trial subject, or her legally acceptable representative, is fully informed about the nature and objectives of the trial and possible risks associated with participation. The investigator will obtain written informed consent from each subject or the subject's legally acceptable representative before any study-specific activity is performed. The informed consent form used in this trial, and any changes made during the course of the trial, must be prospectively approved by the IRB before use. The investigator will retain a copy of each subject's signed consent form.

### **12.4. Subject Confidentiality**

Study records with the study participant's information for internal use at the clinical sites will be secured at the study site during the study. At the end of the study, all records will continue to be kept in a secure location. There are no plans to destroy the records.

Study participant data, which is for reporting purposes, will be stored at the Coordinating Center. Data will identify participants by the unique study identification number. The study data entry and study management systems used by clinical sites and by Coordinating Center research staff will be a secured, password protected computer.

### **12.5. Sample and Data Storage**

Data collected for this study will be analyzed and stored at the Coordinating Center. After the study is completed, de-identified data will be stored at the Coordinating Center for use by researchers for future analyses with the participant's approval. The results of these future analyses will not be made known to the participant.

## **Appendix A: Contingency Operation Plan in Case of Reduced Availability of Study Medication**

The following changes may be implemented and/or adapted in response to disruptions in study medications (salsalate and/or placebo) availability. Information explaining any departures from the current protocol due to unavailability, or limited availability of study medication will be documented in the subject's research record. Changes to study medication dose and visit schedules will be documented on the protocol deviation log with a notation that the change in dose or schedule is because of change in medication availability. The notation will permit the study team to censor those protocol changes that were made because of medication shortages (versus, non-adherence for example) and these events will ultimately be reported separately from other protocol deviations.

### **1. New subject enrollment**

Enrollment of new subjects (Screening Visit 1) may be paused until the investigator is notified that adequate supplies of study medications are available. Eligible participants who have not yet completed Visit 2 (randomization, assignment, and initiation of study medication) will have Visit 2 postponed. The protocol currently allows for Visit 2 to take place up to 180 days after Visit 1. If Visit 2 must be delayed for more than 180 days due to unavailability of study medication, then baseline laboratory measures performed at Visit 1 will be repeated at Visit 2. A delay of over 365 days would require that all Visit 1 screening measures be repeated prior to Visit 2. Reconsent of the participant would be required in this case.

### **2. Treatment and visit modifications for enrolled participants (Visits 2 to 7)**

The overarching goal of treatment modifications in the setting of limited supplies of study medications will be to keep all participants on at least a minimal daily dose of study medication during their remaining time in the study. The study site staff will collaborate with the research pharmacy to achieve this goal on a case-by-case basis.

The current protocol indicates that participants will be provided with sufficient study medication to last until the next scheduled visit. If this cannot be achieved based on participants' current maximally tolerated dose of the study medication, then the shipment schedule, or amount of medication shipped may be adjusted. Examples include sending less than the full number of tablets (e.g., sending a 2 month versus 3 month supply), or sending fewer tablets to provide a lower dose over a period of 3 months. Similarly, changes to treatment (dosing of study medications) and visit schedules will be individualized with consideration to a number of factors including:

- the current dose of study medication being taken
- the number of doses of study medication currently in the participant's possession
- the number of study visits completed/number of study visits remaining
- the expected time to resolution of the study medication supply shortage

Modifications in the event that supplies of study medication are limited or unavailable include, but are not be limited to the following:

- Participants will NOT return unused study medication after each visit/receipt of new study medication. Instead, they will be permitted to continue to use study medications

until the bottles are empty. This instruction will be documented in the participant's research record.

- To avoid gaps in exposure to study medication and to increase the likelihood of reaching 12 months of exposure to study medication the dose of study medication may be reduced, generally to  $\frac{1}{2}$  of the maximally tolerated dose, (up to 6 tablets per day), with further reductions as necessary to the minimum of 1 tablet per day).
- When study medication becomes available, the dose will be titrated back to the prior maximally tolerated dose according to the current study medication titration schedule (beginning with the participants' current dose and up-titrating to the maximally tolerated dose). Participants will be reminded that study medication can cause changes in blood glucose levels and changes to the dose of study medication may require adjustments to their insulin doses. Regular glucose monitoring will be encouraged. These instructions are consistent with the current protocol and consent document.
- If participants are without study medication at any dose for a period of 3 consecutive months, at any point between visit 2 and 6, the study team will consult with the DSMB to determine whether the participant should be scheduled for an early final visit (visit 7), or whether the participant should simply be withdrawn from further participation.
- Participants who have completed visit 6, and who do not have an adequate supply of study medication to remain on their maximally tolerated dose until visit 7 will either
  - reduce their daily dose of study medication so that the number of tablets available extends to the opening of the Visit 7 window. Visit 7 should be scheduled as early in the window as possible
  - complete visit 7 prior to the opening of the visit 7 window. This could include completing all Visit 7 measures at Visit 6 if it is clear that NO study medication will be available to the participant after completing visit 6

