## 2. TRIAL OUTCOMES

**Primary outcome:** Change from baseline to month 12 in the intraepidermal nerve fiber density (IENFD) at the distal thigh.

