#### 5.2.4. Compliance

The number of tablets dispensed at each visit will be recorded in the case report form. Subjects are reminded to return all unused study medication at each visit in the original container. The study staff will collect all unused medications and record the number of tablets remaining. Discrepancies between expected versus actual study medication returned will be evaluated by the local study staff to address issues related to non-adherence to the study protocol. Subjects will be encouraged to continue on the maximally tolerated dose of study medication for the duration of the treatment period. Consistent with the intention to treat model, all subjects will be followed for the duration of the study treatment period according to the treatment schedule, unless consent is withdrawn, or, in the opinion of the investigator, it is unsafe for the subject to continue participation.

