### Analysis of Primary Outcome:

The primary outcome is change from baseline to 12 months in IENFD at the distal thigh. A general linear model will be fitted to the change in IENFD score with factors for treatment group, baseline HbA1c ( $\leq 8.0\%$  or  $> 8.0\%$ ), and baseline IEFND as fixed covariates. If the distributional

assumptions are not met, transformations of IENFD or the use of nonparametric methods will be employed. Sensitivity analyses will be performed to assess how subjects who withdrew may affect conclusions of the analysis. An intent-to-treat analysis set (including subjects who are randomized, treated and have a baseline IENFD) will be used to assess treatment effects with multiple imputation methods employed to impute outcomes for subjects with missing post-baseline data. Depending on the extent and pattern of missingness, other simpler sensitivity analyses may be used: for example, change from baseline to month 12 for subjects completing the study (completers) may be analyzed using an analysis of variance model. The model will include the same covariates that are included in the primary analysis.

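### In a drug shortage, Appendix A allows the primary biopsy to be taken months early or not at all, in conflict with the follow-up rule in 5.2.4 and the month-12 endpoint

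*Combined protocol and SAP*

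**What the plan says.** Section 2 defines the primary outcome as "Change from baseline to month 12 in the intraepidermal nerve fiber density (IENFD) at the distal thigh", and section 10.2 repeats the time point. Table 1 places Visit 7 at month 12 with a window of 14 days either side, counted from the start of medication.

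Section 5.2.4, citing intention to treat, says that "all subjects will be followed for the duration of the study treatment period according to the treatment schedule". Its only exceptions are withdrawal of consent and the investigator's judgement that continuing is unsafe. Section 6.5 is wider: the investigator or sponsor may also withdraw a subject for behavioural or administrative reasons.

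Appendix A, part 2, has two branches for a shortage:

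- **Gap between Visits 2 and 6.** The trigger is worded "If participants are without study medication at any dose for a period of 3 consecutive months, at any point between visit 2 and 6". In that case staff ask the DSMB whether to hold an early final visit or "whether the participant should simply be withdrawn from further participation".
- **After Visit 6, with too few tablets to stay on the tolerated dose.** The participant either stretches the tablets to the Visit 7 window or may "complete visit 7 prior to the opening of the visit 7 window". The text adds: "This could include completing all Visit 7 measures at Visit 6 if it is clear that NO study medication will be available".

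The appendix opens by noting that the shortage may concern salsalate, placebo or both. Departures are logged and reported apart from other deviations.

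The primary model in 10.2 contains treatment, HbA1c stratum and baseline IENFD. Multiple imputation is planned for missing post-baseline data. Nothing is said about a biopsy taken before the Visit 7 window.

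**The concern.** Running out of drug is neither a withdrawal of consent nor a safety judgement, so under 5.2.4 such a participant stays in follow-up and is biopsied at month 12. Under Appendix A the same participant may be biopsied at month 9 or earlier, or may leave with no final biopsy. Staff cannot follow both texts.

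Three things are at stake. First, primary outcomes may be lost from people who would have attended, in a trial that needs 50 evaluable subjects. Second, if the shortage concerns one product, early or missing outcomes could concentrate in one arm, which is a risk of bias as well as of imprecision. Third, the treatment of an early biopsy would be settled later: 10.2 leaves open whether it counts as a month-12 value, is set to missing, or makes the participant a completer for the sensitivity analysis.

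**Working it through.** **1. How early.** Visit 6 is at month 9, so final measures taken there are 12 − 9 = 3 months early, and about 11.5 − 9 = 2.5 months before the Visit 7 window opens. In the gap branch, a literal reading starts the three months at day 0, giving a final visit at about month 3, or 9 months early. If the first supply (3 months plus 14 days) is used up first, it falls at about 3.5 + 3 = month 6.5, or 5.5 months early.

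**2. The texts side by side for a consenting participant without drug.**

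| Text | Final biopsy |
|---|---|
| 5.2.4 | Follow-up continues to the end of the period |
| 6.5 | May be withdrawn for an administrative reason |
| Appendix A, gap branch | Early final visit, or withdrawal; no criterion |
| Appendix A, after Visit 6 | In the Visit 7 window on stretched tablets, or before it; no rule between the two |
| 10.2 | Month 12; silent on an earlier biopsy |

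**3. The plan's power.** Inputs from section 10.1: difference 1.65 fibers/mm, SD 2.0, two-sided 5% t-test, 25 per group. The noncentrality is 1.65 / (2.0 × √(1/n₁ + 1/n₂)) with n₁ + n₂ − 2 degrees of freedom. For 25 and 25 it is 2.917 against a critical value of 2.011, and power is 81.5%. The stated 81% is reproduced.

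**4. Power if final biopsies are missing.** The fractions below are assumptions, since the documents give none. Imputation keeps these subjects in the analysis set. I assume that it adds little information on month-12 IENFD, so they are counted as lost.

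| Lost from 25 and 25 | Left per group | Power |
|---|---|---|
| 0% | 25 | 81.5% |
| 10% | 22.5 | 77.2% |
| 20% | 20 | 72.0% |
| 30% | 17.5 | 65.9% |

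The recruitment target is a fairer base. With 70 recruited and 20% attrition, 70 × 0.8 = 56 remain, or about 34 and 22 at 3:2, with power 84.2%. Losing a further 20% leaves 56 × 0.8 = 44.8, about 27 and 18, with power 75.5%. The true split will differ somewhat, because subjects enrolled before August 2017 were randomized 1:1.

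**5. Can an early biopsy predict the month-12 value?** Sections 6.2, 6.3 and 9.5 provide for two biopsies at baseline and two at the final visit, four in all. An early final visit replaces the month-12 one. No participant would then have both an early and a month-12 IENFD, and the relation between them cannot be estimated from the trial.

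**The case against.** The case on the other side has real force, and much of it stands.

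- **A contingency with safeguards.** The stated aim of Appendix A is to keep participants on some drug. One of the two options after Visit 6 still reaches the Visit 7 window, and departures are logged separately. This limits how often the problem arises, but a deviation log is not an analysis rule.
- **Section 6.5 permits administrative withdrawal.** This is true, so Appendix A is not out of line with every section. It means that 5.2.4 and 6.5 also need reconciling with each other.
- **Section 10.2 does not count an early biopsy as month 12.** A reader might infer that it does, because the appendix calls the visit Visit 7 and the model has no time term. The section is silent, and such a value could equally be set to missing.
- **The DSMB.** A reader might infer that a board aware of treatment differences would steer the choice, since section 3 says the 2017 change was made "by recommendation of the DSMB to address differential study medication discontinuation rates and to increase the number of subjects exposed to study drug". That suggests the board knew discontinuation by arm. Nothing shows that it saw IENFD by arm or would use a participant's assignment. It is independent, it is consulted only in the gap branch, and the listed factors for individual changes include neither arm nor outcome.
- **Early timing and the effect.** A reader might also infer that early biopsies themselves shrink the effect. If the difference builds up linearly, moving 20% of biopsies to month 9 gives 1.65 × (1 − 0.2 × 3/12) = 1.57 and 77.5% power, and moving them to month 6 gives 1.65 × (1 − 0.2 × 6/12) = 1.49 and 73.0%. Those figures reflect lost exposure. A participant whose drug ends at month 9 has built up 1.65 × 9/12 = 1.24, and a month-12 biopsy off drug would show that at best. An early on-drug value could even overstate the month-12 intention-to-treat effect.

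**Conclusion.** The concern holds as a conflict over outcome collection and a gap in the analysis rules. Following Appendix A as written can produce off-time or missing primary outcomes among people still willing to be measured, possibly unequal by arm. The plan does not say how off-time values are handled.

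The extent is unknown. The drops from 81.5% to 72.0% and from 84.2% to 75.5% rest on an assumed 20% loss, on the plan's 1.65 and SD 2.0, and on imputation recovering little. Bias by arm is a possibility and has not been shown. The documents do not support saying that the DSMB's knowledge biases the choice, or that early measurement in itself reduces the effect. The sponsor should amend the text; the point does not invalidate the design.

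**What to change.** **Appendix A, 5.2.4 and 6.5.** Reconcile the three on outcome collection only. State that lack of study drug does not by itself end outcome follow-up, and that Visit 7 measures are sought at month 12 (±14 days) from everyone who still consents. Remove the per-participant choice between measuring and withdrawing. Dosing in a shortage is outside this point.

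**Section 10.2, or the detailed SAP that section 10 promises before the blind is broken.** State that a biopsy taken before the Visit 7 window is not the month-12 value in the primary analysis. Handle month 12 as missing under the planned multiple imputation, and add a sensitivity analysis that uses the early value as observed. Do not use the early value as an imputation predictor unless an explicit assumption links it to month 12. Say also whether such participants count as completers.

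**Cost.** A short edit to the appendix, aligned wording in two sections, and a few sentences on analysis. Some month-12 biopsies will be off drug, so the intention-to-treat effect may be smaller than 1.65 and the change does not guarantee the planned power. Imputation that borrows from participants still on drug may be optimistic for those who had run out, which is a further reason to collect month-12 biopsies where possible.
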